### **4.3 Interim Analyses**

There have been three interim analyses performed to support interim CSRs. The first interim CSR was dated 14 February 2012 (amended 10 January 2013). A second interim CSR was dated 17 September 2013 (amended 06 March 2015). The third interim CSR was dated 11 November 2015.

## **5. SUBJECT DISPOSITION**

Subject disposition will be tabulated overall and for each subpopulation. The number of subjects screened and in each analysis population will be summarized. The number and percentage of subjects who complete the study will be summarized, along with the number and percentage of subjects who do not complete the study for each discontinuation reason as specified on the eCRFs.

## **6. PROTOCOL DEVIATIONS**

The number and percentage of subjects who have major protocol deviations during the study will be summarized overall and for each deviation reason for the Safety Population.

Protocol deviations will be presented by subject in a data listing.

## **7. DEMOGRAPHIC AND BASELINE CHARACTERISTICS**

Demographic and baseline characteristics at study entry will be summarized by subpopulation and overall for the Safety Population.

Variables to be summarized are:

- Continuous variables
  - Age (years)
  - Weight (kg)
  - Height (cm)
  - Body mass index (BMI) (kg/m^2)
  - Body surface area (BSA) (m^2)
  - Previous daily dose of Cystagon (mg/m^2/day)
  - Total daily dose of RP103 (average % of previous Cystagon dose)
  - WBC cystine level (nmol ½ cystine/mg)
- Categorical variables
  - Age category (young child, child, adolescent, adult)
  - Gender
  - Race

---

- Ethnicity
- WBC cystine levels ( $\leq 1$ ,  $> 1$  to  $\leq 2$ ,  $> 2$  nmol  $\frac{1}{2}$  cystine/mg)

For subjects who completed study RP103-03, baseline height is taken from the RP103-03 Screening Visit. For subjects who did not complete study RP103-03, baseline height is the last available observation prior to the first dose of study drug in RP103-04. For all other parameters, baseline is as defined in Section 4.2.1.

Medical history information will be summarized by MedDRA system organ class (SOC) and preferred term (PT) by subpopulation and overall for the Safety Population.

## 8. PHARMACOKINETIC, PHARMACODYNAMIC AND

### 8.1. Pharmacodynamics

WBC cystine concentration levels (nmol  $\frac{1}{2}$  cystine/mg) will be summarized over time using descriptive statistics (number of subjects, mean, geometric mean, median, standard deviation, coefficient of variation, minimum, and maximum) for the PK/PD Population for each subpopulation and overall. Summaries will be provided for both analysis visits and collected visits. WBC cystine concentration levels will also be summarized over time by baseline WBC cystine levels ( $\leq 1$ ,  $> 1$  to  $\leq 2$ ,  $> 2$  nmol  $\frac{1}{2}$  cystine/mg) for both analysis visits and collected visits.

### 8.2. Pharmacokinetics

Plasma cysteamine concentration (mg/L) will be summarized over time using descriptive statistics (number of subjects, mean, geometric mean, median, standard deviation, coefficient of variation, minimum, and maximum) for the PK/PD Population for each subpopulation and overall. Summaries will be provided for both analysis visits and collected visits.

A large black rectangular redaction box covers the top half of the page. On the left side, there is a white rectangular area containing several black horizontal bars of varying lengths, suggesting redacted text or data.

complete study RP103-03, baseline is the last non-missing assessment prior to the first dose of study drug in study RP103-04.

A series of horizontal black bars of varying lengths and positions on a white background, suggesting redacted text or a heavily redacted document. The bars are irregular in length and position, creating a fragmented appearance. There are also a few small, isolated black squares and a short vertical line on the left side.

## 9. SAFETY ANALYSES

Safety summaries will be produced for the Safety Population for each subpopulation and overall.

### 9.1. Study Drug Exposure

Duration of study drug exposure will be calculated as the duration from the date of first dose of RP103 in Study RP103-04 to the date of last dose as:

Exposure (days) = (Last Dose Date – First Dose Date + 1) – number of days dosed with Cystagon

Duration of exposure will be summarized for each subpopulation and overall using descriptive statistics. The number and percentage of subjects with duration of exposure in each category ( $\leq$  12 months,  $>$  12 months and  $\leq$  24 months,  $>$  24 months and  $\leq$  36 months,  $>$  36 months and  $\leq$  48 months,  $>$  48 months and  $\leq$  60 months, and  $>$  60 months) will also be summarized.

The mean RP103 dose (mg/m^2/day) will be summarized over time using collected visits.

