### **Screening**

The Screening visit may occur up to 28 days prior to Day 1.

Medical and medication histories and clinical laboratory assessment (hematology, chemistry, urinalysis), physical examination (including basic neurological and skin assessments) and vital signs, ECG, body weight, body mass index (BMI), body surface area (BSA), adverse events determination, concomitant medications, an Investigator administered [REDACTED]

[REDACTED] will be made according to the Schedule of Events, Appendix 14.1.

All adult patients or parent or guardian of pediatric patients will begin completing a daily diary medication log, recording the dose and time, of cysteamine medications, proton pump inhibitors (PPI) and other gastric acid reducing drugs (prescription and over the counter medications).

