### **Dose Confirmation Period (Days 1-5)**

This period entails 3 study visits over 5 days, required only for patients that did not complete Study RP103-03.

- **Day 1:** If this visit is more than 7 days after the Screening date, some assessments must be repeated as specified in the Schedule of Events. This is a morning study visit while the patient is fasted, with pre-dose (within 15 minutes

prior to the first RP103 dose) blood samples collected for trough cysteamine and peak WBC cystine determination while the subject is still taking Cystagon®. RP103 treatment regimen begins at the clinic on the morning of Day 1, administered Q12H at a starting RP103 total daily dose equal to 70% of the Screening total daily dose of Cystagon®.

- **Days 4 and 5:** Each day includes a morning visit. 0.5 hour (30 minute) post-dose blood samples for plasma cysteamine (PK) and WBC cystine (PD) determination will be collected. RP103 Q12H treatment regimen continues at the starting total daily dose. Once the Investigator receives WBC cystine results for the Dose Confirmation Period, and RP103 dose adjustment may be prescribed so that it can be implemented before the subject returns for their next study visit (Quarterly Visit 1).

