### **8.5. Study Treatment Administration and Compliance**

All study treatments administered in the clinic will be under the supervision of clinic personnel. Patients not entering the trial from Study RP103-03 will be started on twice a day administration of RP103, where the total daily RP103 dose is 70% of their total daily stable Cystagon® dose.

If during the study any patient does not achieve a meaningful reduction of WBC cystine level (i.e., < 1 nmol ½ cystine/mg protein) or does not tolerate the dose, as determined by the Investigator, the patient may have their RP103 dose adjusted or may be terminated from the study.

A daily diary of cysteamine and gastric acid reducing medications will be maintained throughout the study.

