**Individual patient dosing will be stopped if:**

- A patient exhibits a treatment-emergent adverse event of Common Terminology Criteria for Adverse Events (CTCAE) grade 3 or higher and not likely related to the underlying disease.

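### SAP 9.1 removes Cystagon days from RP103 exposure but counts days on neither product as RP103 exposure

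*SAP*

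**What the plan says.** SAP 9.1 defines "the duration from the date of first dose of RP103 in Study RP103-04 to the date of last dose as" follows: "Exposure (days) = (Last Dose Date – First Dose Date + 1) – number of days dosed with Cystagon". The result is summarised with descriptive statistics by subpopulation and overall. The section also reports "The number and percentage of subjects with duration of exposure in each category", with cut points at 12, 24, 36, 48 and 60 months.

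The formula contains one deduction, for Cystagon. SAP 9.1 has no rule for days on neither product or for days on both, and does not say which product the last dose refers to. SAP 4.2.8 says only that missing data are not imputed.

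The protocol collects the relevant information. Section 8.5 states: "A daily diary of cysteamine and gastric acid reducing medications will be maintained throughout the study". Under section 6.1.2, patients not coming from RP103-03 "begin completing a daily diary medication log, recording the dose and time, of cysteamine medications" from Screening.

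**The concern.** If the measure were elapsed time from first to last dose, Cystagon days would stay in. If it is time on RP103, every day off RP103 should come out. The formula does neither: it removes a day off RP103 when Cystagon replaced it and keeps the day when nothing did.

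Days off drug are foreseeable. Protocol 10.1.1 lists a condition under the words "Individual patient dosing will be stopped if", namely a treatment-emergent event of grade 3 or higher that is not likely related to the underlying disease. The causality categories in Protocol 10.2 refer to rechallenge, so stopping and restarting is contemplated. Time off drug because of poor tolerability would then be reported as time on drug.

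The primary objective is long-term safety and tolerability. Readers of the crude adverse event percentages will use the exposure table to judge how long patients were treated.

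**Working it through.** **Inputs.** The formula and categories come from SAP 9.1. The documents state no exposure figure to reproduce and no gap lengths, so the gaps of 7 to 90 days below are assumptions. SAP 9.1 does not define a month. Categories were checked at 30.4375 days per month and at 30, the spacing of the analysis windows in SAP 4.2.9.

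**Step 1: same interruption, two results.** Take two patients with a 400-day span from first to last RP103 dose and 60 days off RP103 within it. Each has 400 − 60 = 340 days on RP103.

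- Cystagon taken on the 60 days: 400 − 60 = 340. Correct.
- Nothing taken on the 60 days: 400 − 0 = 400. Overstated by 60 days, and 60/340 = 17.6%.

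**Step 2: size by gap and span.** With span *T* and untreated gap *g*, the formula gives *T*, the days on RP103 are *T* − *g*, and the relative overstatement is *g*/(*T* − *g*).

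| Gap (days, assumed) | 400-day span | 760-day span |
|---|---|---|
| 7 | 1.8% | 0.9% |
| 14 | 3.6% | 1.9% |
| 30 | 8.1% | 4.1% |
| 60 | 17.6% | 8.6% |
| 90 | 29.0% | 13.4% |

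For longer spans and a 60-day gap:

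- 60 months (about 1,826 days): 60/1,766 = 3.4%.
- 96 months (about 2,922 days): 60/2,862 = 2.1%.

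**Step 3: categories.** At 30.4375 days per month, 400 days is 13.1 months and 340 days is 11.2 months. At 30 days per month they are 13.3 and 11.3. Either way the patient is placed in >12 to 24 months instead of ≤12 months. A 96-month span with a 60-day gap stays in the >60 month category (2,862/30.4375 = 94.0 months), so its category is unaffected.

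**Step 4: where the number is used.** SAP 10 states that annualised exposure-adjusted adverse event analysis will not be done. SAP 9.2 bases adverse event percentages on the number of subjects in the Safety Population. Exposure in days is therefore not a denominator for the planned event rates.

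**The case against.** **Gaps may be rare or absent.** Protocol 10.1.1 does not say whether stopped dosing may resume, and Protocol 7.3 lists illness that prevents further treatment as a reason for withdrawal. If stopping is permanent, the interval ends and no gap arises. This limits what can be said about frequency, and the documents do not show that any patient is affected. It does not remove the point, since the rechallenge wording in Protocol 10.2 contemplates restarting and the formula has no rule for that case.

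**Elapsed duration is a legitimate measure.** It is, and it is simple and robust to poor diaries. But the formula as written is not elapsed duration, because Cystagon days are taken out.

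**The effect is small in a long study.** For patients treated for years this is right, as Step 2 shows. It matters mainly for shorter spans and near category boundaries.

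**A stronger reading that does not hold.** A reader might infer that exposure is also understated, or even negative. Cystagon days are not expressly limited to the interval, and the protocol places Cystagon use outside it. For patients not from RP103-03, Protocol 6.1.2 says "The Screening visit may occur up to 28 days prior to Day 1", and some patients return to Cystagon before the End of Study visit. From this a reader might further conclude that subpopulations B and C are not comparable with A. The documents do not support these conclusions. The lead-in sentence defines the span as starting at the first RP103 dose, so the Cystagon days to subtract from it are naturally those inside it. On that reading no Screening days are deducted and no negative value arises. If the last dose means either product, days after a switch back cancel: with 9 such days, (400 + 9) − 9 = 400. Even if a programmer wrongly deducted all the outside days the schedule allows (28 before Day 1 plus up to 9 after RP103, 37 in total), a negative value would need a span under 37 days, and no such patient is shown. What remains is a wording clarification. Day 1 may also be a day on both products, because the pre-dose sample is for "peak WBC cystine determination while the subject is still taking Cystagon". Deducting that day would cost one day (399 instead of 400).

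**Conclusion.** The point holds on any reading of SAP 9.1: untreated days inside the dosing interval count as RP103 exposure, while Cystagon-treated days do not. The direction is overstatement. For an assumed 60-day gap it is +17.6% with a change of category on a 400-day span, about +3.4% at 60 months and about +2.1% at 96 months. How many patients are affected, and by how much, cannot be determined from the documents. The consequence is confined to the descriptive exposure summary and its categories. Claims of understated or negative exposure, or of subpopulations B and C not being comparable with A, should not be made.

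**What to change.** Replace the formula in SAP 9.1 with:

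Exposure (days) = (last RP103 dose date − first RP103 dose date in RP103-04 + 1) − days within that interval documented as having no RP103 dose, whether or not Cystagon was given.

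Add three conventions:

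- A day with any RP103 dose counts as exposed. This settles Day 1 and switch days.
- A blank diary day is not treated as unexposed. Protocol 8.4 anticipates diary non-compliance, and counting only diary-confirmed dosing days would bias exposure downward.
- Elapsed first-to-last RP103 dose duration is shown beside the new measure, so that readers can see how much interruption was removed.

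Naming RP103 for both dates and limiting deductions to the interval also settles the open wording. In the Step 1 example both patients then have 340 days, and a patient with no interruption is unchanged.

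The cost is a few lines of SAP text, one derived variable and an extra summary in the exposure table. The diary already asks for dose and time of cysteamine medications. The downside is small: undocumented interruptions remain counted as exposure, which a footnote to the table should state.

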#### 5.1.1. Primary Objective

- To assess safety and tolerability of long-term repeat dosing of RP103 in patients with cystinosis.

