##### **Monthly Study Visits**

Only patients who completed Study RP103-03 will attend Monthly Visits. These visits will be made monthly ( $\pm$  7 days) after study entry according to the Schedule of Events, Appendix 14.1. A minimum of six (6) consecutive Monthly visits will be completed for each patient. Clinical laboratory assessments (hematology, chemistry, urinalysis), physical examination (including basic neurological and skin assessments) and vital signs, ECG, body weight, body mass index (BMI), body surface area (BSA), an Investigator administered [REDACTED]

[REDACTED] will be made according to the Schedule of Events. During these visits, blood samples for PK (cysteamine) and PD (WBC cystine) will be collected 0.5 hour post RP103 dose administered at the clinic. Patients or parents will continue to maintain a daily diary, recording the dose and time, of cysteamine medications, proton pump inhibitors (PPI) and other gastric acid reducing drugs (prescription and over the counter medications). Patients or their parents will return their completed daily diary at each scheduled study visit and will receive a new or re-dispensed daily diary. Concomitant medications and adverse events will be collected.

At or before each Monthly Visit, the Investigator will review available safety and PK/PD data and if a patient does not achieve an appropriate level of WBC cystine reduction or does not tolerate the dose, the patient may have their RP103 dose adjusted or may be terminated from the study. This review will be documented in source and in the CRF as appropriate, with the action(s) taken and reasons for such action(s).

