### 1.2. Objectives of Statistical Analysis

The objective of this Study is to assess the long-term safety, tolerability, pharmacokinetics and pharmacodynamics of RP103 in pediatric and adult subjects with cystinosis.

The primary objective is to assess safety and tolerability of long-term repeat dosing of RP103 in subjects with cystinosis.

Secondary objectives include assessment of steady-state pharmacokinetics (PK) and pharmacodynamic (PD) of RP103 and [REDACTED]

This statistical analysis plan (SAP) describes the efficacy and safety analyses that will be performed, based on the study protocol amendment 9 dated 18NOV2015. This amendment (Version 2.0) of the SAP adds details about the statistical analysis to be performed. Changes from Version 1.0 of the SAP including the following:

- updated Sponsor from Raptor Therapeutics to Horizon Pharma
- updated protocol version for study
- added a description of visit windowing and visit mapping methods
- added a description of variables to be summarized for subject disposition
- added variables to be summarized for demographics and baseline characteristics
- added a summary of protocol deviations
- added details for pharmacokinetic and pharmacodynamics summaries
- [REDACTED]
- [REDACTED]
- added a summary of study drug exposure
- added details for adverse event summaries
- added details for summaries of other safety parameters including labs (added shift tables), ECG, vital signs, and concomitant medications

Any changes from the SAP will be described in the clinical study report (CSR).

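### The readable SAP plans no count of RP103 dose reductions or interruptions, and days on neither product count as RP103 exposure

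*SAP*

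**What the plan says.** Protocol 5.1.1 gives the primary objective as "To assess safety and tolerability of long-term repeat dosing of RP103 in patients with cystinosis", and SAP 1.2 repeats it.

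Protocol 8.5, with the visit sections in 6.1.2 and 9.1, has one provision for two situations: WBC cystine not low enough, or a dose that the patient cannot tolerate. In either case the dose may be adjusted or the patient withdrawn. Protocol 4.5 describes upward steps of about 10%. Protocol 10.1.1 has individual dosing stopped for certain adverse events of grade 3 or higher.

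On recording, protocol 6.1.2 says of the investigator's monthly review: "This review will be documented in source and in the CRF as appropriate, with the action(s) taken and reasons for such action(s"). Protocol 8.5 adds: "A daily diary of cysteamine and gastric acid reducing medications will be maintained throughout the study".

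SAP 9.1 plans three summaries:
- duration of exposure, running "from the date of first dose of RP103 in Study RP103-04 to the date of last dose", less the "number of days dosed with Cystagon";
- the number of subjects in 12-month duration bands;
- the mean RP103 dose in mg/m²/day, which "will be summarized over time using collected visits".

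SAP 7 adds one RP103 dose variable to the baseline table. Among AE consequences, SAP 9.2 tabulates only discontinuation of the study. Protocol 11.1 asks for AE summaries by drug discontinuation, and the readable items in SAP 10 do not list a change on this.

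**The concern.** A dose change in this study can mean two opposite things. An increase for cystine control says little against tolerability. A reduction or a pause because of vomiting is itself a tolerability outcome. Only the direction of the change and its reason separate the two, and the plan reports neither.

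The patient who would be missed stays in the study on a reduced or interrupted dose. The adverse event is tabulated, but no planned summary shows that the prescribed dose could not be kept up. A stable dose over the years could then be read as good long-term tolerability when the documents give no basis for that reading. Gastrointestinal events are where this matters most: in the RP103-03 crossover, protocol Table 7 shows 24 related gastrointestinal episodes on RP103 against 8 on Cystagon.

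The exposure formula raises a smaller question. It accepts that days without RP103 should come out, but removes only those on which Cystagon was taken instead.

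**Working it through.** The plan states no figure on this point, so there is nothing to reproduce. The check has three parts.

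**1. What is recorded against what is reported.**
- Dose action and reason at review: documented under protocol 6.1.2; no summary in SAP 9.1 or 9.2.
- Dosing stopped for an AE while the patient stays in the study: foreseen in protocol 10.1.1; SAP 9.2 counts it only if the patient leaves the study.
- AEs by drug discontinuation: asked for in protocol 11.1; SAP 9.2 has study discontinuation instead.

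**2. What dose by visit can show.** Assume 60 subjects (the protocol's maximum), all at 1000 mg/m²/day.
- 12 reduced by 10% and 12 raised by 10%: mean = (12 × 900 + 12 × 1100 + 36 × 1000) / 60 = 1000. The SD due to the changes is √(24 × 100² / 59) = 63.8.
- 12 reduced by 20% and 24 raised by 10%: mean = (12 × 800 + 24 × 1100 + 24 × 1000) / 60 = 1000.

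SAP 4.2.1 calls for N, mean, median, SD and range for continuous variables, so the spread should be shown too. It helps little, because patients differ in dose from the start. Protocol Table 2 gives a daily Cystagon dose of 1,849 ± 536 mg, a relative SD of 536 / 1849 = 29%. Assume the same relative spread for RP103 per m², that is, an SD of 290 on a mean of 1000, and dose changes unrelated to starting dose. The first pattern then moves the SD only from 290 to √(290² + 63.8²) = 297. A minimum shows that someone is on a low dose, not that anyone was reduced.

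Growth adds ambiguity. If the dose is divided by current BSA (SAP 9.1 does not say), a child on a fixed dose whose BSA goes from 1.17 m² (the RP103-03 mean) to an assumed 1.40 m² shows a change of 1.17 / 1.40 − 1 = −16.4% with no dose action at all.

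**3. Exposure formula.** Let T be the days from first to last dose and g the days on neither product. The formula counts T, RP103 was taken on T − g days, and the overstatement is g / (T − g).

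| Gap g (assumed) | T = 365 | T = 1826 |
|---|---|---|
| 14 days | 14/351 = 4.0% | 14/1812 = 0.8% |
| 30 days | 30/335 = 9.0% | 30/1796 = 1.7% |
| 60 days | 60/305 = 19.7% | 60/1766 = 3.4% |

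If Cystagon covers a 30-day gap in one year, the formula gives 365 − 30 = 335 days, which is correct. That gap is not counted as exposure, but it is not reported as an interruption either.

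**The case against.** The strongest case is that tolerability is already well covered. SAP 5 tabulates discontinuation reasons. SAP 9.2 gives related, serious and grade 3 or higher events, severity, year of onset, and gastrointestinal events split into 1–3 and 4 or more episodes. SAP 9.6 counts use of gastric-acid-reducing drugs, which SAP 10 makes a safety endpoint. A patient with repeated vomiting who stays in the study would appear in the episode table. This stands, so a reader who infers that intolerance never surfaces in the results goes too far. What these outputs do not show is whether the dose had to be cut or paused.

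Second, the table and listing titles in SAP 12.1 and 12.2 are redacted, as is one item in SAP 10, and protocol 11.1 says in general terms that drug administration will be summarized. A dosing table or listing cannot be excluded. The point therefore rests on the readable text of SAP 9.1 and 9.2, which is where such an analysis would be defined.

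Third, the data may be incomplete. Entry in the CRF is only as appropriate, the quarterly text in protocol 6.1.2 for RP103-03 completers does not mention the CRF, and nothing readable says that diary days are entered in the database. This stands and limits the fix.

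Fourth, a reader might infer that inflated exposure dilutes the AE rates. The documents do not support that: SAP 10 drops the exposure-adjusted rates, and the percentages in SAP 9.2 use numbers of subjects.

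**Conclusion.** The point holds in a limited form. The readable SAP does not identify subjects who stayed in the study on a reduced or interrupted RP103 dose, gives no reasons for dose changes, and does not summarize the AEs that led to them. Dose by visit cannot stand in for this, even with the SD and range. Days on neither product are counted as RP103 exposure.

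The size is unknown, because no document gives the frequency of reductions or of gaps. The unchanged mean is a constructed example: it shows that offsetting is possible, not that it will occur, and a mean moves when reductions outweigh increases. The exposure error is small over long follow-up (0.8% to 3.4% over five years for gaps of 14 to 60 days) and affects only the descriptive duration and its bands. It would be wrong to infer that every interruption counts as exposure, since those bridged with Cystagon are subtracted.

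The change is worth making because it bears directly on the primary objective at little cost.

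**What to change.** Change the analysis only; no dosing or stopping rule is affected.

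- **SAP 9.1:** add n (%) of subjects, by subpopulation and overall, with at least one RP103 reduction for intolerance, at least one interruption, and at least one increase for WBC cystine. Use the recorded actions and reasons where the CRF holds them, with a category for reason not recorded.
- **SAP 9.2:** add AEs leading to dose reduction, to interruption and to drug discontinuation, by SOC and PT. If the drug-discontinuation summary in protocol 11.1 is to be dropped, list that in SAP 10.
- **Exposure formula:** subtract documented RP103 interruption days as well as Cystagon days, counting a day that is both only once. Do not treat a blank diary day as an interruption, because that could understate exposure.

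Time to first reduction and the size of each change are optional.

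The cost is SAP wording and one or two tables. Exposure figures become slightly shorter, and the counts are only as complete as the capture of dose actions in the CRF, which the report should state.
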